## 6.7 Criteria for delay of boost vaccination and/or stop for boost vaccination

After enrollment, subjects may encounter clinical circumstances that warrant a delay in the administration of the subsequent vaccination of investigational vaccine/placebo. These situations are listed below:

- Individuals with a clinically significant active infection (as assessed by the investigator) or axillary temperature ≥37.3°C or oral temperature ≥38.0°C, within 3 days before intended investigational vaccine/placebo vaccination. Or other clinical symptoms/diseases that may be considered inappropriate for vaccination by the investigator
- Individuals who received any other vaccines within 21 days before planned vaccination.

If a subject meets a criterion for delay of vaccination, the subject may receive trial vaccination, if the subject is otherwise eligible for trial participation even if the window period of vaccination visit has passed. The decision to vaccinate in those situations will be taken by the investigator.

In this trial, the second vaccination may be stopped in some circumstances. These circumstances include systemic anaphylaxis or severe hypersensitivity reactions following the prime vaccine/placebo administration. If these reactions occur, the subject must not receive additional vaccinations; however, the subject is encouraged to continue in trial participation for safety reasons.

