# 9.1.6 Blood sample and urine sample collection

Blood samples will be collected at each site visit: ie, at Screening Visit for eligibility screening tests (clinical laboratory testing, see Section 9.1.6.3), at Visits 2, 3 and 6 for routine safety laboratory testing (see Section 9.1.6.4 for Visits 2, 6 coagulation function test, Visits 2, 6, 11 thyroid function test). Blood samples for immunogenicity (anti-S1/anti-RBD IgG and SARS-CoV-2 neutralizing antibody) will be collected at Visits 1, 5, 6, 8, 10, 11 and 12 for adults and at Visits 1, 5, 6, 8, 11 and 12 for the elderly (see Section 9.1.6.5).

Should a blood sampling be performed during a vaccination visit, this sampling must occur before the injection of the investigational vaccine or placebo. Serum sample will be collected for women of childbearing potential at Screening Visit and Visit 5 before each investigational vaccine/placebo injection for pregnancy testing (see Section 9.1.9). Figertip blood samples will be collected at Screening Visit for SARS-CoV-2 serostatus determination (see Section 9.1.6.1) and HIV serostatus determination (see Section 9.1.6.2).

Urine samples will be collected for all subjects at Screening Visit for eligibility screening (see Section 9.1.6.3), and at Visits 2, 3 and 6 for routine safety laboratory testing (see Section 9.1.6.4).

All samples will be collected in accordance with acceptable laboratory procedures. Samples of immunogenicity and CMI testing will be processed and stored at the study site as described in the provided Laboratory Manual.

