## 9.1.6.5 Immunogenicity assessment

Serum immunogenicity (humoral immunity / antibody) is detected by ELISA and neutralizing antibody test. Each blood sample for ELISA assessments will be approximately 7.5 mL, and for neutralizing antibody test will be approximately 7.5 mL.

Should a blood sampling be performed during a vaccination visit, this sampling must occur before the vaccination of the investigational vaccine or placebo.

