# 13.1.1 Analysis sets

- Safety Set: Safety Set will consist of all randomized subjects who receive at least one dose of the investigational vaccine/placebo and at least one safety evaluation.
- Total Vaccinated Cohort (TVC): According to intention-to-treat analysis set principle, the TCV will include all randomized subjects who have received at least one dose of the investigational vaccine/placebo and can provide with effective baseline.
- Per protocol set (PPS): The PPS will include all subjects in the TVC who have no major protocol violations and complete boost vaccination. The protocol violation criteria will be defined as part of the blinded data review. The categories of major protocol violations include:
  - 1 not meeting inclusion criteria, or meeting exclusion criteria,
  - 2 receiving a wrong investigational vaccine/placebo,
  - 3 receiving prohibited therapies,
  - 4 other major protocol violations that be identified during blinded data reviews.

All summaries and analyses of safety data will be based on subjects in the Safety Set.

The primary immunogenicity endpoint analyses will be based on the PPS and TVC, and secondary immunogenicity endpoint analyses will be based on the TVC.

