- (7) **Physical Examination**: including general, skin and mucosa, lymph gland, head, neck, spine, extremities, nervous system, and other.

6 Analysis Sets

(1) Total Vaccinated Cohort (TVC)

According to intention-to-treat principle, TVC is defined as all randomized subjects who have received at least one dose of IMP and have at least one post-baseline functional antibody titer immunogenicity assessment.

(2) Per Protocol Set (PPS)

PPS is defined as all subjects included in TVC who have no major protocol deviations and receive boost vaccination. The protocol deviation criteria are a part of the blinding data review. Major protocol deviations include:

- \checkmark Violation of major inclusion or exclusion criteria,
- ✓ Assignment to incorrect vaccine/dose,
- ✓ Intake of prohibited concomitant medication
- ✓ Other major protocol deviations identified during blinding data review.

Immunogenicity analysis at Day 7 and Day 21 after prime and boost immunization will be based on both TVC and PPS. Immunogenicity persistence analysis for Month 3, 6 and 12 after prime immunization will be based on the evaluable subjects in TVC. The analysis of exploratory endpoints will be only based on TVC subjects.

(3) Safety Set (SS): is defined as all subjects who received at least one dose of IMP.

SS consists of total SS, SS for prime immunization (referred to as SS1), and SS for boost immunization (referred to as SS2). Safety analysis for each dose will be based on the vaccinated subjects of each

dose, respectively. SS1 is defined as all subjects received the prime immunization. SS2 is defined as all subjects received the boost immunization.

All above analysis sets will be determined after the discussion of pricinple investigator, project manager, statistician and data manager in data blind review meeting before database lock.

7 Statistical Methods

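### The single per-protocol set requires the boost even at Day 21 post-prime, where the sample precedes the boost, and it leaves boost timing undefined after the boost

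*SAP*

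**What the plan says.** **Definition.** SAP section 6 gives one PPS: "PPS is defined as all subjects included in TVC who have no major protocol deviations and receive boost vaccination". Protocol 13.1.1 has the same boost condition: "The PPS will include all subjects in the TVC who have no major protocol violations and complete boost vaccination".

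**Where it is used.** SAP section 6: "Immunogenicity analysis at Day 7 and Day 21 after prime and boost immunization will be based on both TVC and PPS". Later visits are handled differently: "Immunogenicity persistence analysis for Month 3, 6 and 12 after prime immunization will be based on the evaluable subjects in TVC". Exploratory endpoints also use the TVC only.

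**Samples.** Under protocol 9.1.6, antibody samples "will be collected at Visits 1, 5, 6, 8, 10, 11 and 12 for adults". The elderly list is the same without Visit 10. Protocol 9.1.6.5 adds that, at a vaccination visit, "this sampling must occur before the vaccination of the investigational vaccine or placebo".

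**Boost timing.** The schedule of activities puts the boost at Day 22 ±2 days. Protocol 6.7 allows a subject who meets a listed delay criterion to be boosted "even if the window period of vaccination visit has passed", at the investigator's decision. It states no maximum delay.

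**Deviations.** The named major deviations in SAP section 6 are eligibility, wrong vaccine or dose, and prohibited medication. An open category follows: "Other major protocol deviations identified during blinding data review". Protocol 14.4 refers specific deviations to the medical monitoring plan, which is not among the documents. SAP 7.1.3 analyses data by scheduled visit.

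**The concern.** A titre drawn before the second injection cannot be affected by whether that injection is given. The PPS rule nevertheless lets the later event decide whether the earlier titre counts.

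The later event may not be neutral. Protocol 6.7 stops the boost after systemic anaphylaxis or severe hypersensitivity to the first dose. Protocol 6.6 suspends vaccination in a cohort when a DLT criterion is met. Protocol 11.1 lets the SRC decline the boost for a dose cohort. The Day 21 post-prime PPS estimate is then conditioned on having tolerated the prime well enough to go on, which is not the question at that time point.

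After the boost the difficulty is a missing rule. The objectives concern two doses 21 days apart, but nothing in the PPS definition says how far from 21 days the interval may be. Nor does it say how far from the boost a nominal 7-day or 21-day sample may fall.

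**Working it through.** **The plan's own figure.** The only design calculation (SAP 4.3) is the chance of at least one TEAE among 24 subjects at an 8% rate: 1 − 0.92^24 = 0.8648, against a stated 86.5%. It reproduces and has no bearing on the PPS. The documents give no expected PPS size and no rate of missed or late boosts.

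**Step 1: which time points are affected.** The PPS is used at Day 7 and Day 21 after each dose. Day 7 post-prime is a listed endpoint (SAP 5.1) but has no scheduled antibody sample, because Visit 3 is not in the sampling list. That leaves Day 21 post-prime (Visit 5, Day 22, before injection) as the one post-baseline, pre-boost time point.

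**Step 2: precision lost at Day 21 post-prime.** SAP 7.1.1 uses a t-based interval on log titres, so the half-width in units of the log-titre SD is t(0.975, n−1)/√n. I assume 24 subjects per arm with no other exclusions, and m subjects sampled at Visit 5 but not boosted:

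| m | share of arm | PPS n | half-width (SD) | widening |
|---|---|---|---|---|
| 0 | 0% | 24 | 0.422 | none |
| 1 | 4.2% | 23 | 0.432 | 2% |
| 2 | 8.3% | 22 | 0.443 | 5% |
| 3 | 12.5% | 21 | 0.455 | 8% |
| 5 | 20.8% | 19 | 0.482 | 14% |
| 24 (SRC withholds the cohort's boost) | 100% | 0 | no estimate | – |

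**Step 3: possible shift.** If the dropped subjects differ from those retained by d on the log10 scale, the PPS mean differs from the mean of all 24 by (m/24) × d. With assumed values:

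- m = 1, d = 0.3: 0.0125, a GMT ratio of 10^0.0125 = 1.03.
- m = 3, d = 0.5: 0.0625, a GMT ratio of 10^0.0625 = 1.155.

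Both d and its sign are unknown.

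**Step 4: post-boost intervals.** The windows are boost Day 20–24, Visit 6 Day 29 ±3 = Day 26–32, and Visit 8 Day 43 ±4 = Day 39–47.

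- In-window boost: Visit 6 falls 26 − 24 = 2 to 32 − 20 = 12 days after it, and Visit 8 falls 39 − 24 = 15 to 47 − 20 = 27 days after.
- Boost 7 days late (Day 29): Visit 6 falls from 3 days before to 3 days after the boost, and Visit 8 falls 10 to 18 days after.
- Boost 14 days late (Day 36): the whole Visit 6 window falls 4 to 10 days before the boost.

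The two late cases assume that later visits stay tied to Day 1. The documents do not say whether they do. If visits move with the boost, this misalignment disappears, but the departure from the 21-day dose interval remains.

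**Step 5: the SAP's own precedent.** For safety, SAP section 6 separates SS1 (received the prime) from SS2 (received the boost) and analyses each dose on its own recipients. Immunogenicity has no counterpart.

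**The case against.** **The TVC is the safeguard.** A subject with a Visit 5 titre and no boost meets the SAP's TVC definition and is reported at the same time point. Conditioning on completing the regimen is what a per-protocol set does, and the regimen here is prime plus boost. This stands as a limit on the harm, because no sample disappears from the trial's results. It does not make the Day 21 post-prime PPS meaningful, and the SAP commits to reporting that set.

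**The stakes are modest.** Immunogenicity is secondary, SAP 7.1 plans no formal testing, and the primary safety objective uses other analysis sets. The number of subjects affected could be zero. All of this stands.

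**The PPS does not govern every visit.** A reader might infer from the single definition that it does. It does not: Months 3, 6 and 12 use the TVC.

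**Late-boosted subjects are not shown to stay in the PPS.** A reader might infer that because protocol 6.7 permits a late boost, it cannot be a deviation and the subject must be kept. The documents do not support this. The permission covers only subjects who meet a listed delay criterion and are otherwise eligible. Protocol 6.9 requires any discontinuation of vaccine to be documented as a deviation whatever the reason, so an act can be allowed and still be a deviation. The open category in SAP section 6, or the medical monitoring plan, could class late boosts as major. What remains is that the SAP states no rule and leaves the matter to the blinded review.

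**A timing rule conditions on a post-prime event too.** Listed reasons for delay include fever and infection. This is correct and is a cost of the change.

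**Conclusion.** The concern holds for Day 21 post-prime. The rule as written removes valid pre-boost titres from the PPS because of a later event that may relate to tolerability. If the SRC withholds a cohort's boost, the rule empties that cohort's PPS at the last time point before the decision takes effect. The effect is confined to the PPS, to one time point and to secondary endpoints.

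For 0 to 3 missed boosts per arm the loss is 0 to 12.5% of the arm and up to about 8% in interval width. These counts are assumptions, and the direction of any shift cannot be determined.

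For post-boost time points the finding is narrower: the effect of boost timing and of the boost-to-sample interval on PPS membership is not pre-specified. The documents neither require nor rule out keeping late-boosted subjects.

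Both matters are worth correcting because the remedy is cheap. Neither threatens the primary objective.

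**What to change.** Define the PPS by time point in SAP section 6, following the SS1/SS2 pattern.

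1. **Post-prime time points:** TVC members with no major deviation, with no boost condition. State also that discontinuing vaccine before the boost, which protocol 6.9 records as a deviation, does not by itself exclude a subject here. Otherwise the boost condition could return by that route.
2. **Post-boost time points:** keep the boost condition, and state before unblinding how the prime-to-boost and boost-to-sample intervals affect evaluability. One option is the protocol's own windows: boost at Day 22 ±2 and sample within its visit window, with late-boosted subjects kept in the TVC.
3. **Visit scheduling:** say whether post-boost visits are counted from Day 1 or from the actual boost date, since Step 4 of the working depends on it.

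The cost is SAP wording and table footnotes, with PPS denominators that differ by time point. The post-boost PPS may lose a few subjects, and the timing rule itself conditions on what happened after the prime, so PPS results should be read beside the TVC. This is an analysis-set rule only and takes no position on when, or whether, a boost may be given.

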7.1 General Considerations

No formal statistical testing will be conduct in this study.

7.1.1 General Analysis Method

Descriptive Statistics

Unless otherwise specified, the following descriptive statistics will be provided according to the type of variable:

- ✓ Continuous variables will be summarized by mean, standard deviation (SD), median, minimum (min) and maximum (max).
- ✓ Category or ordinal variables will be summarried by the number and percentage, where the percentage will be calculated based on the number of subjects in the corresponding analysis set as denominator and may be presented with exact 95% Clopper-Pearson CIs.

Additionally, descriptive statistics of titer and fold increase of titer will include geometric mean and its two-sided 95% confidence interval (CI). The geometric mean titer (GMT) is calculated as the mean of the logarithm of the functional antibody titers, back-transformed into the original scale. Two-sided CIs will be obtained by calculating CIs using Student's t-distribution for the mean of the logarithmically transformed assay results and transforming the limits back to the original scale.

Geometric mean fold rise (GMFR) is calculated as the mean of the difference of logarithmically transformed assay results (post vaccination time point – pre vaccination time point) and back-transformed into the original scale. Two-sided CIs will be obtained by calculating CIs using Student's t-distribution for the mean difference of the logarithmically transformed assay results and transforming the limits back to the original scale.

Decimal Places

Unless otherwise specified, the decimal places will follow the following rules:

- \checkmark The decimal places of min, max, median, Q1 and Q3 are consistent with the original data.
- ✓ The decimal places of mean, GM, SD and 95% CI are 1 more than the original data.
- ✓ Keep 2 decimal places in the percentage.

- ✓ Keep 2 decimal places in coefficient of variation (CV) and geometric coefficient of variation (GCV).
- ✓ Keep 4 decimal places if the p value is no less than 0.0001, and present as "<0.0001" if the p value is less than 0.0001.

- ✓ Keep 3 decimal places for all testing statistics.
- ✓ Keep 2 decimal places for the derived data.

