  of titer detection, the positive conversion is defined as the antibody titer reaching at least 4 times of the lower
  limit.

Safety analysis: Within 14 days after each vaccination (Including the day of vaccination of vaccine/placebo), by collecting soliciting AE, including local reactions (Vaccination site: pain/tenderness, erythema/redness, induration/swelling) and general reactions (nausea, vomiting, diarrhea, headache, fatigue/tiredness, myalgia, arthralgia, chills loss of appetite, malaise and fever), to evaluate reactogenicity. In addition, body temperature (axillary) as indicator of reactogenicity will be collected (with fever defined as axillary temperature  $\geq 37.3^{\circ}$ C, oral temperature  $\geq 38.0^{\circ}$ C).

For each solicited reaction, including fever, the percentage of subjects will be summarized by event severity for each day within 14 days after each vaccine/placebo vaccination and overall.

All AEs and SAEs will be coded using the Medical Dictionary for Regulatory Activities (MedDRA version 23.0) and summarized by system organ class (SOC) and preferred term (PT) for each group (BNT162b1 and placebo) including aggravation after vaccination and new medical conditions.

Safety summaries will be provided by different age groups and different dose cohorts/placebo groups.

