# Please note:

Diary cards will be the only source document allowed for remote collection of solicited local and systemic reactions (including body temperature measurements). The following additional rules apply to the documentation of safety information collected by diary card:

- o Diary cards should be reviewed with the subject.
- No corrections or additions to the diary card will be allowed after it is reviewed with the investigator/designee.
- O Any data that are identified as implausible or incorrect, and confirmed by the subject to be a recording error should be corrected by the subject on the diary card (the correction should include a single strikethrough line and should be primeed and dated by the subject).
- Any blank or illegible fields on the diary card not otherwise corrected as above will be missing in the eCRF.
- The study site should enter all readable entries on the diary card into the eCRF.
- O Any newly described solicited safety information should be added to the diary card by the subject and primeed and dated. Any new unsolicited safety information would be recorded in the subject source document as a verbally reported event and therefore captured as an AE and recorded in the AE eCRF.
- Starting on the day of vaccine/placebo administration, the subject will check for specific types of events at the vaccination site (solicited local reactions), any specific generalized symptoms (solicited systemic reactions), body temperature (axillary), any other symptoms or change in the subject's health status, and any medications taken. These solicited reactions and body temperature will be recorded in the diary. Assessments should preferably take place in the evening at day's end using the same method of measurement every day.
- Temperature measurement is to be performed using the thermometer provided by the study site. If the subject feels unusually hot or cold during the day, the subject should

- check his/her temperature. The highest body temperature measured that day should be recorded on the diary card.
- The measurement of solicited local reactions (pain/tenderness, erythema/redness, and induration/swelling) is to be performed using the ruler provided by the study site. If multiple measurements are taken during the day, the highest measured value should be recorded on the diary card.

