- > TEAEs leading to discontinuation by SOC and PT
- Related TEAEs leading to discontinuation by SOC and PT
- Unrelated TEAEs leading to discontinuation by SOC and PT
- ➢ AESIs by SOC and PT
- Related AESIs by SOC and PT
- Unrelated AESIs by SOC and PT
- ➢ TESAEs by SOC and PT
- Related TESAEs by SOC and PT
- > Unrelated TESAEs by SOC and PT

The DLT AE and related DLT AE will be summaried by group. The distribution of severity, injection stage, occurrence will be provided for TEAEs and related TEAEs. The episodes of AEs, number and percentage of subjects with TEAEs will be summarized by worst grade by PT nested within SOC.

For each solicited reaction (including fever), the number and percentage of subjects with TEAEs within 14 days after each immunization will be summarized by severity and overall.

TEAE after each immunization will be summarized based on Safety Set for prime and boost immunization, respectively.

The following TEAEs will be listed by subject: related TEAEs, unrelated TEAEs, TEAEs leading to discontinuation, AESIs and SAEs.

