7.9 Handling of Missing Data

This study is Phase I dose-exploratory study, therefore the missing data in this study will not be handled.

7.10Timing of Statistics Analyses

Prime analyses will be conduct based on all available safety and immunogenicity data when all subjects in each age group complete Visit 9 (Day 50, 28 days after boost vaccination). Update analyses will be conduct when all subjects in each age group complete Visit 11 (Month 6 after prime immunization), Visit 12 (Month 12 after prime immunization).

Unblinding will be conduct along with the prime analysis of immunogenicity and safety at 28 days after boost immunization, but the subjects will be kept blinded.

Version History

Version	Date	Author	Changes & Rationale
V1.0	2020-08-28		Initial version.
V1.1	2020-10-29		Add laboratory analysis according to the Appendix C Table 4: Laboratory abnormality grading scale

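### Solicited-reaction percentages divide by every subject given the dose, with no rule for missing diaries, so subjects without diary data can count as non-reactors and rates may be understated.

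*SAP*

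**What the plan says.** - **Denominator.** SAP 7.1.1 sets the default for categorical summaries: "the percentage will be calculated based on the number of subjects in the corresponding analysis set as denominator".
- **Which set.** SAP 6 defines SS1 as everyone who received the prime dose and SS2 as everyone who received the boost. SAP 7.6.1 applies them: "TEAE after each immunization will be summarized based on Safety Set for prime and boost immunization, respectively". For each solicited reaction it asks for the number and percentage within 14 days of each dose, by severity and overall, and names no other denominator.
- **Missing data.** SAP 7.9: "the missing data in this study will not be handled".
- **Source of the data.** Protocol 9.3.4 makes the diary card the sole source for solicited reactions collected away from the site, and adds: "Any blank or illegible fields on the diary card not otherwise corrected as above will be missing in the eCRF".
- **Daily rates.** The safety analysis paragraph of the protocol synopsis says that, for each solicited reaction, "the percentage of subjects will be summarized by event severity for each day within 14 days after each vaccine/placebo vaccination and overall". Protocol 13.1.4 and SAP 7.6.1 give only 14-day summaries.

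**The concern.** Solicited local and solicited systemic reactions are two of the three primary endpoints (Protocol 5.2.1). Under the stated rule a dosed subject stays in the denominator whether or not there is any information on reactions, but can enter the numerator only if a reaction was recorded. With no information, the subject is arithmetically a non-reactor.

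This pulls rates in one direction, downward, and by more points where reactions are common. With similar missingness in all groups, the vaccine-placebo difference shrinks by the same proportion. The trial is meant to show that responses in Chinese subjects are comparable with those seen abroad (Protocol 4.2.6), so a downward pull on reactogenicity bears on that comparison.

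The SAP already uses the idea of an evaluable subject: SAP 6 restricts the immunogenicity persistence analysis to evaluable subjects in the TVC. It has no counterpart for solicited reactions.

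**Working it through.** **1. The plan's own figure.** SAP 4.3 assumes 24 subjects per dose cohort and a TEAE rate of 8%, giving an 86.5% chance of seeing at least one. Check: 1 − 0.92^24 = 0.8648, which reproduces it. The figure takes all 24 as evaluable. With 22 it is 1 − 0.92^22 = 84.0%, and with 20 it is 1 − 0.92^20 = 81.1%.

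**2. Effect of the denominator rule.** Let p be the true rate and m the number of the 24 with no solicited data, assumed unrelated to whether they reacted.

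- Expected percentage under the SAP rule: p × (24 − m)/24.
- Expected percentage among evaluable subjects: p.
- Relative understatement: m/24, which is 4.2%, 8.3% and 16.7% for m = 1, 2 and 4.

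The illustrative rates are those cited from the US study in Protocol 4.2.4.1. The values of m are assumptions, since neither document gives a missing-diary rate.

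| Reaction (US study) | True rate | m = 0 | m = 1 | m = 2 | m = 4 |
|---|---|---|---|---|---|
| Pain, 30 µg, dose 2 | 100% | 100% | 95.8% | 91.7% | 83.3% |
| Pain, 10 µg, dose 2 | 83.3% | 83.3% | 79.8% | 76.4% | 69.4% |
| Fever, 30 µg, dose 2 | 75% | 75% | 71.9% | 68.8% | 62.5% |
| Pain, 10 µg, dose 1 | 58.3% | 58.3% | 55.9% | 53.5% | 48.6% |
| Fever, 10 µg, dose 2 | 8.3% | 8.3% | 8.0% | 7.6% | 6.9% |

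The 75% row shows the arithmetic: 0.75 × 23/24 = 0.719, 0.75 × 22/24 = 0.688, 0.75 × 20/24 = 0.625.

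**3. Interval, m = 4 with 15 recorded events** (exact Clopper-Pearson):

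- All 24 as denominator: 15/24 = 62.5% (40.6% to 81.2%).
- Evaluable 20 as denominator: 15/20 = 75.0% (50.9% to 91.3%).
- All four without data counted as reactors: (15 + 4)/24 = 79.2%.

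The upper limit, which matters most for safety, is 91.3 − 81.2 = 10.1 points lower under the SAP rule.

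**4. Difference from placebo.** Pain after dose 2 in the US study was 100% at 30 µg and 16.7% on placebo, a gap of 83.3 points. With two of 24 missing in each group it becomes 83.3 × 22/24 = 76.4 points.

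**5. Where the site does not back up the diary.** In the schedule of activities (Protocol Table 2) the prime dose is followed by a visit at 24 h. The boost is not: after the 1, 3 and 6 h checks on Day 22, the next visit is Visit 6 on Day 29 ±3 days, so Day 26 at the earliest. Protocol 4.2.4.1 reports that in the US study most reactions peaked 2 days after vaccination and had resolved by day 7, with fever usually gone within a day. For a Day 22 boost the peak falls at about Day 24, when only the diary is recording.

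**The case against.** **Site contact recovers some reactions.** Local reactions are assessed at 1, 3 and 6 h and at each visit through Day 50. Temperature is taken at the same hours and at visits. Adverse events since the last visit are asked about every time, and diaries are reviewed with the subject. A blank day also does no harm to a 14-day any-occurrence percentage if the reaction is recorded on another day. This stands. A reader might infer that every subject without a diary is counted as reaction-free, and the documents do not support that. The gap is mainly in systemic symptoms and fever arising between visits; local reactions are less exposed.

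**The denominator is not the whole Safety Set.** A reader might think subjects who miss the boost dilute the post-boost rates. They do not, because post-boost summaries use SS2.

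**The two Safety Set definitions differ.** SAP 6 says the Safety Set "is defined as all subjects who received at least one dose of IMP", while Protocol 13.1.1 also requires at least one safety evaluation. It is tempting to blame this, but Protocol 9.3.4 keeps every vaccinated subject on site for at least 6 hours with vital signs. Almost everyone would meet the protocol's condition, and it would not remove a subject without a diary.

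**The time course can still be examined.** SAP 7.1.2 derives onset day and duration, and SAP 7.6.1 reports the distribution of occurrence. The table mock-ups are a separate attachment that is not available here. It would be too strong to say the foreign time course cannot be checked, or that the SAP alone dropped the daily rates: the each-day percentage is explicit only in the synopsis, and Protocol 13.1.4 agrees with the SAP.

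**An evaluable-only denominator has its own bias.** If subjects with reactions fill in diaries more reliably, rates move up. The analyses are also purely descriptive (SAP 7.1). Both points are fair. They argue for showing more than one denominator, not for leaving the rule unstated.

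**Conclusion.** The concern holds in this form: for solicited reactions after each dose, the SAP divides by all of SS1 or SS2 with no rule for missing diary data, so a dosed subject without diary data after the vaccination day and without a site-recorded reaction counts as a non-reactor. Rates may be understated by a relative m/24. At 75% that is 3.1, 6.2 or 12.5 points for 1, 2 or 4 such subjects.

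This rests on three assumptions: all 24 subjects receive the dose in question; m, which the documents do not give; and missingness unrelated to reaction status. With complete diaries the loss is zero, so a reader should not infer that the results are understated, only that the plan neither prevents nor reveals it. The 75% is illustrative: the US study counted fever from 38.0 °C, whereas this trial uses an axillary threshold of 37.3 °C. The exposure is largest for systemic symptoms and fever after the boost.

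**What to change.** In SAP 7.6.1:

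1. For each solicited reaction and dose, use as denominator the SS1 or SS2 subjects with at least one diary entry for that reaction after the vaccination day. The 1, 3 and 6 h site checks alone should not make a subject evaluable. Otherwise nearly everyone qualifies for local reactions and fever, and the denominator returns to all dosed subjects.
2. Show the number evaluable, and the number with no diary and with a partial diary, by group.
3. Keep the percentage on all of SS1 or SS2, including site-recorded reactions, as a lower bound. Add a sensitivity count treating subjects without data as reactors.
4. Reconcile the synopsis with Protocol 13.1.4 and SAP 7.6.1 by adding the daily table by severity for the 14 days, with subjects having an entry that day as denominator.

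The cost is SAP wording, one or two extra tables and a slightly smaller N. The evaluable rate may carry a small upward bias if subjects with reactions complete diaries more often; the lower bound in item 3 makes that visible. No new data collection is needed.
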